### 14.2 Baseline Evaluation and Procedures

#### 14.2.1 Pre-Procedure/Baseline Assessments

Below pre-procedure assessments and data collection must be performed prior to the ablation procedure.

- **Patient Information and Consent** (procedure must be done within 60 days of consent)
- **Demographics** (age, gender, etc).
- **Medical history**, including but not limited to arrhythmia, heart disease, thromboembolic events, lung/respiratory problems.
  - o **AF history** (first evidence of AF, number of episodes, symptoms, etc).
  - o **NYHA Functional Class Scale**.
  - o **CHA2DS2 VASc Score**. Subjects will be scored against the CHA2DS2 VASc.

- **Vital signs** (length, weight, etc.)
- **Medication history:** Medication history (cardiac medication, AAD medication, anticoagulation regimen and any other clinically significant medication history) shall be gathered by interview or from medical records following enrolment but prior to the ablation procedure and should be recorded in the eCRF.
- **Anticoagulation therapy:** Uninterrupted anticoagulation management is mandatory for each study subject. For subjects on warfarin/coumadin therapy, subjects shall be maintained on Warfarin/Coumadin for at least 3 weeks prior to treatment with an INR  $\geq 2$  (to be confirmed maximum 48h hours pre-procedure). Any INR  $<2$  within 3 weeks prior to ablation will lead to exclusion of the patient or postponement of the study procedure. The results must be available prior to start of procedure.
- **Pregnancy test** must be done on all women of childbearing age and potential within 72-hours prior to the procedure and documented in the subject's medical chart.
- **Imaging (TTE or other acceptable equivalent cardiac imaging – i.e. CT/MRI) within 6 months prior to procedure to assess the LA and LVEF.** Must be collected within 6 months prior to procedure, in case of the imaging assessment is older than 6 months LA/LVEF, dimensions shall be re-measured during the index procedure prior to insertion of the study catheter. In case of re-measurements before study catheter insertion fail to meet the LA and/or LVEF criteria, the subject will be considered as not meeting eligibility and will be excluded.
- Imaging for **detection of left atrial thrombus** or other structural contraindications to an ablation procedure is mandatory the day before or the day of the ablation procedure. Presence of a thrombus will require postponement of the ablation procedure or may even lead to exclusion of the subject from further study involvement. The imaging method to be used for atrial thrombus detection is TEE, Intracardiac Echocardiography (ICE), Cardiac CT or MRI
- **Electrocardiogram** (12-Lead ECG). Data from 12-lead ECG recordings will be collected if performed standard of care.
- **Adverse Events** must be collected from the time the subject signs the informed consent onwards.
- Quality of life via the **Atrial Fibrillation Effect on Quality-of-Life (AFEQT™)** questionnaire (non-Standard of Care). Note: Patient questionnaires will only be used in countries with validated languages
- **Cardiac CT/MRA** is required to be performed within 6 months prior to the ablation procedure to assess the structure and size of the PVs and the left atrial anatomy.

Additional Assessments for Wave I subjects:

- **Cerebral MRI, Neurological Exam and Neurological Evaluation using the MMSE, NIHSS and mRS (non-SOC)** are required to be performed within 72-hours pre-procedure (for procedures on Monday a window of a maximum of 96 hours is justified) to evaluate the neurological condition and presence of neurological deficits of the subjects before undergoing study ablation procedure. A certified/qualified physician expert must perform neurologic exams at pre-and post-ablation and possibly at other follow-up visits, pending previous findings of micro-emboli/neurologic deficits. Pre-and post-ablation cerebral MRIs will be analyzed by a central core lab to determine the frequency, size, and

anatomical location of cerebral micro-emboli, if any. Note: Patient questionnaires will only be used in countries with validated languages

## 14.2.2 Study Ablation Procedure Guidelines

### 14.2.2.1 Ablation Selections

There are 10 electrodes in the Circular IRE Catheter. The Multi-Channel IRE Generator creates pulsed electrical fields by delivering bipolar and biphasic energy through electrode pairs. Ablating with electrode pairs creates a closed electrical circuit between two adjacent electrodes and between two alternated electrodes. While the generator activates electrodes in groups of adjacent trios, only one electrode pair will deliver energy at a given time.

Ablations can be performed using a minimum of 3 adjacent electrodes or 1 electrode trio, and a maximum of 10 electrodes or 8 electrode trios to target desired regions of tissue. Multiple electrode trios can be activated during an ablation. When selecting multiple electrodes, the system will automatically activate electrode trios (up to two trios) in between the selected electrode trios to prevent gaps. For example, if you select electrode trios 1 3 and 4 6, the system will automatically activate electrode trios 2 4 and 3 5. See Figure 4 for an example of electrodes activated in adjacent trios. To activate all electrodes at once, use the All Electrodes toggle, as shown in Figure 5

The system delivers energy in pulses. The quantity of pulses is determined by the PFA levels: Min or Max. To adjust the level of energy delivered to the tissue, select the desired PFA level prior to starting ablation.

[figure not shown]

Figure 4: Electrode Selection

[figure not shown]

Figure 5: All Electrodes Toggle

Functional parameters and user adjustable settings for the device(s) are presented in table 4.

Table 4: Investigational Device- Functional Parameters and User adjustable settings

Functional Parameters	
Electrodes*	Adjacent + Alternate per trio
Type of Pulse	Bipolar, biphasic
PFA Measurement	900V between adjacent electrodes 1800V between alternated electrodes
Ablation Time	<1sec
Idle and Irrigation flow	4ml/min
User adjustable settings	
Pre-ablation time	Range 0-2 sec (0/1/2)
Post-ablation time	Range 0-2 sec (0/1/2)
Min/Max PFA Level	Max PFA level is twice the number of pulses than in Min PFA level
Electrode Trio(s)	User to select electrode trio(s) to activate

#### 14.2.2.2 Study Ablation Procedure Sequence & Guidelines

Subjects will arrive to the EP laboratory for their ablation procedure and will undergo preparation for the procedure per the hospital's standard protocol (discretion of investigator).

#### Electrophysiology Study, Mapping and Ablation Procedure

- Preparation:
  - Anesthesia or sedation should be delivered per standard EP lab procedure.
    - It is highly recommended to ensure presence of anesthesiologist during the procedures.
  - The use of an appropriate strategy to minimize risk of esophageal injury (temperature probe, CARTOSOUND® and/or ICE, barium swallow) is OPTIONAL.

- The type of monitoring method/device and clinical practice associated with the observations of this data will be collected in the CRFs.
- Placement of diagnostic catheters:
  - Coronary sinus catheter in the CS for pacing purposes
  - Other catheters may be placed at the discretion of the investigator
- At the discretion of the investigator, introduce an Intracardiac Echo (ICE) probe to review LA anatomy and PVs
- Administration of heparin bolus prior to or immediately after transeptal puncture.
- A single or double transeptal puncture should be performed per standard EP lab (at the discretion of the investigator).
- Mapping:
  - Following successful transeptal puncture, a left atrial map is required before ablating,
    - Wave I: it's highly recommended to use the Circular IRE catheter, possible substituted by the use of Lasso®, PentaRay® or 3D rotational angio (at investigator discretion).
    - Wave II: utilizing the Circular IRE Catheter, Lasso®, PentaRay®, or 3D rotational angio (at investigator discretion).
  - Create a voltage map, if SOC
- PVI:
  - Confirm targeted ACT 350-400 seconds. Systematic anticoagulation with heparin should be administered with ACT level checked on regular basis during the procedure to ensure an ACT target range of 350-400 seconds.
  - Introduction of the 8.5 F compatible sheath, if not used for mapping.
  - Introduce the Circular IRE Catheter as per IFU, if not used for mapping.
  - Advance and position the Circular IRE Catheter at the targeted PV.
  - When position is satisfactory, commence energy delivery with the Circular IRE Catheter.
    - Recommended workflow:
      - a) Left pulmonary veins and carina position and ablate with contracted and wider loop
      - b) **MANDATORY:** prior to ablation in the region of the right sided PVs, precautionary measures to evaluate the proximity to the phrenic nerve.
        - Evaluate the diaphragm while pacing the phrenic nerve.
        - Assure diaphragmatic capture PRIOR to voltage delivery.
      - c) Right pulmonary veins position and ablate with contracted and wider loop
    - Use the maximum PFA level. Consider using the minimum PFA level when repeated applications are applied. Use clinical judgment and consider patient anatomy and the catheter position to determine if minimum PFA level should be used.
    - Do not allow ablation electrodes to overlap during application of PFA energy. Doing so may cause an error message to appear and stop the ablation before completion. In case of overlap, change the catheter position or turn off overlapping electrodes on the monitor to perform ablation.
  - All subjects will undergo PV ablation with the Circular IRE Catheter until PVI is achieved in all targeted PV'.
    - IRE ablation is to be used as the primary mode for PVI.

- If isolation is not obtained after circular PFA applications described above, review remaining signals and deliver PF energy with corresponding electrodes.
- ONLY after the investigator deems IRE ablation unable to achieve PVI should the lab be switched to commercial RF setup to complete the procedure (PVI only). Note, to prevent any risk to the patient, the IRE system should be completely disconnected prior to use of an RF system.
- Confirmation of entrance block (and exit block if SOC) (PVI) of all clinically relevant targeted PVs.
  - To verify entrance block, analyze electrograms in coronary sinus and/or atrial paced rhythm to confirm that no PV potentials are present.
- Ablation outside the PV region is NOT allowed with IRE ablation modality (further details below).
- Post PVI:
  - Administer adenosine/isoproterenol for each clinically relevant targeted PV to rule out dormant conduction
    - If any, treat reconnected PV regions by reviewing remaining signals on reconnection location and deliver PF energy with corresponding electrodes.
  - Confirmation and documentation of final entrance block (exit block is optional) (PVI) of all clinically relevant targeted PVs
    - To verify entrance, analyze electrograms in coronary sinus and/or atrial paced rhythm to confirm that no PV potentials are present.
    - Wave I: use Circular IRE Catheter AND Lasso® or PentaRay® for confirmation
    - Wave II: use Circular IRE Catheter, Lasso® or PentaRay® for confirmation per investigators choice
  - The ablation procedure is considered complete when confirmation of entrance in clinically relevant targeted PVs is confirmed.
  - Recommendation: after confirmation of final entrance block (exit block is optional) block, evaluate diaphragmatic capture while pacing the phrenic nerve.

#### Ablation outside the PV region

- **Prophylactic** ablation outside the PV region (in example SVC, roofline, CTI) is NOT allowed.
- If an arrhythmia requiring ablation outside the PV is identified.
  - **prior** to insertion of the study catheter (consistent with exclusion criteria) investigators will be required to switch to the commercial setup using a commercially available Biosense Webster catheter used with a commercially available RF generator. The subject will be considered a screen failure (<ICF signature or excluded from the study (> ICF signature).
  - **after** insertion of the study catheter, the subject will undergo PVI with IRE ablation modality followed by commercial RF therapy to complete the procedure (treatment of arrhythmia outside PV region). The subject will be evaluable for acute success but excluded from the long-term effectiveness cohort and followed till 3-months post procedure. Note: Ongoing AE(s) at month 3 shall be followed up until resolution (with or without sequelae).

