### 8.1 Description of the Study Design

The design of the study will be carried out as an interventional, prospective, multicenter, single-arm clinical study. The study will enroll subjects with drug refractory, symptomatic PAF who are candidates for catheter ablation. All study subjects will be followed though 12 months post-ablation.

For the purpose of characterization of safety and to provide preliminary estimates for safety and acute effectiveness of the IRE system, Wave I of the study will enroll up to 40 subjects, who will undergo the index procedure and additional neurological, PV and esophageal assessments. For the purpose of safety and long-term effectiveness Wave II of the study will enroll up to 330 main study phase subjects plus roll-ins. Acute data from Wave I will be assessed for both, preliminary acute safety and acute performance, of the IRE system before proceeding with Wave II. Wave II enrollment can be initiated when all Wave I subjects have

reached 7 days follow up unless the Sponsor deems otherwise per sections 25 (Study Suspension or Termination) and 6.4.2 (Minimization of Risk).

An adaptive Bayesian design to will be used to determine the sample size. Two sample size selection interim analyses will be performed based on the primary effectiveness endpoint. Study success as defined by the main study endpoints will be analyzed for the respective Wave II analysis populations further described in the statistical section of this protocol (section 20). An additional interim analysis will be performed for claiming early trial success when 30 subjects reach full 12-month of follow-up and all subjects reach three months of follow-up.

In Wave II, the first 1-3 subjects for each ablating physician will be considered roll-in subjects to verify consistent workflow for study device components and to minimize any learning curve effects. Operators whom performed procedures in Wave I may be exempted from roll-ins for Wave II per training charter. The roll-in phase will include a maximum of 180 subjects.

Subjects will be evaluated prior to the procedure, prior to discharge, and post procedure at 7 days (Day 7-9), 1 month (Day 23-37), 3 months (Day 76-104), 6 months (Day 166-194), and 12 months (Day 335-379).

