### 8.2.1 Primary Endpoints

- **Acute Safety**

The primary safety endpoint is the incidence of PAEs (within seven (7) days of the initial mapping and ablation procedure). PAEs include the following AEs:

Atrio-Esophageal Fistula*	Phrenic Nerve Paralysis (permanent)
Cardiac Tamponade/perforation	Pulmonary Vein Stenosis*
Device or procedure related death*	Stroke/CVA
Major Vascular Access Complication/Bleeding	Thromboembolism
Myocardial Infarction	Transient Ischemic Attack (TIA)
Pericarditis	

\* Device or procedure related death, pulmonary vein stenosis and atrio-esophageal fistula that occur greater than one week (7 days) post-procedure are considered and analyzed as PAEs.

A 14% performance goal is set for the primary safety endpoint

- **Long term effectiveness:**

Freedom from documented (symptomatic and asymptomatic) atrial arrhythmia (AF, AT or AFL) episodes based on electrocardiographic data ( $\geq 30$  seconds on arrhythmia monitoring device) during the effectiveness evaluation period (Day 91-Day 365). Acute procedural failure (i.e., failure to confirm entrance block, with or without touch-up, in all PVs except those that are silent and/or cannot be cannulated post-procedure) will be considered a long-term effectiveness failure.

A 50% performance goal is set for the primary long-term effectiveness endpoint

Further refer to appendix 1 for definitions on long term effectiveness terms.

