**Table 6: Primary Adverse Events**

Primary Adverse Event	Description / Criteria
Death*	Subject death directly related to the device or procedure and occurs at any time during or after the procedure.
Atrio-Esophageal Fistula*	Defined as a connection between the atrium and the lumen of the esophagus. Evidence supporting this diagnosis includes documentation of esophagus erosion combined with evidence of a fistulous connection to the atrium such as air emboli, an embolic event, or direct observation at the time of surgical repair. A CT or MRI scan is the most common method of documentation of an AEF.
Myocardial Infarction	Presence of any one of the following criteria: 
 
- Detection of ECG changes indicative of new ischemia (new ST-T changes or new Left Bundle Branch Block [LBBB]) that persist for more than 1 hour
 
- Development of new pathological Q waves on ECG
 
- Imaging evidence of new loss of viable myocardium or new regional wall motion abnormality
 

Primary Adverse Event	Description / Criteria

Cardiac Tamponade**/Perforation
	
The development of a significant pericardial effusion during or within 30 days of undergoing the index AF ablation procedure. A significant pericardial effusion is one that results in hemodynamic compromise, requires elective or urgent pericardiocentesis, or results in a 1cm or more pericardial effusion as documented by echocardiography
 
Cardiac tamponade/perforation should also be classified as:                      Early – diagnosed prior to discharge                      Late – following initial discharge from the hospital

Thromboembolism
	
Formation of a clot (thrombus) inside a blood vessel causing obstruction to blood flow accompanied by clinical symptoms. The thrombus can migrate (embolus) and obstruct distal vascular sites.
 
Diagnostic tests to help detect thromboembolisms may include but are not limited to angiography (pulmonary or distal), ventilation-perfusion (V/Q) scans, venography, Doppler ultrasonography, spiral CT, and echocardiography.
 
For the purpose of this study silent (asymptomatic) cerebral embolism will not be considered a PAE.

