
Stroke/Cerebrovascular Accident (CVA)
	
Diagnosis:
 
 
-Rapid onset of a focal or global neurological deficit with at least one of the following: change in level of consciousness, hemiplegia, hemiparesis, numbness or sensory loss affecting one side of the body, dysphasia or aphasia, hemianopia, amaurosis fugax, or other neurological signs or symptoms consistent with stroke.
 
-Duration of a focal or global neurological deficit <math>\geq 24</math> h; or <math>< 24</math> h, if therapeutic intervention(s) were performed (e.g. thrombolytic therapy or intracranial angioplasty); OR available neuroimaging documents a new hemorrhage or infarct; or the neurological deficit results in death.
 
-No other readily identifiable non-stroke cause for the clinical presentation (e.g., brain tumor, trauma, infection, hypoglycemia, peripheral lesion, pharmacological influences). †
 
-Confirmation of the diagnosis by at least one of the following: Neurology or neurosurgical specialist; Neuroimaging procedure (MR or CT scan or cerebral angiography); Lumbar puncture (i.e., spinal fluid analysis diagnostic of intracranial hemorrhage).
 
 
Definition:
 
Stroke: (diagnosis as above, preferably with positive neuroimaging study)
 
 
Minor—Modified Rankin score <math>< 2</math> at 30 and 90 days††
 
Major—Modified Rankin score <math>\geq 2</math> at 30 and 90 days
 

Primary Adverse Event	Description / Criteria
Transient Ischemic Attack	New focal neurological deficit with rapid symptom resolution (usually 1 to 2 h), always within 24h; neuroimaging without tissue injury.
Phrenic Nerve Paralysis	Absent phrenic nerve function as assessed by a sniff test. A phrenic nerve paralysis is considered to be permanent when it is documented to be present 12 months or longer following ablation.
Pulmonary Vein Stenosis*	A reduction of the diameter of a PV or PV branch. Severe PV stenosis ( $\geq 70\%$ reduction in the diameter of the PV) will be considered a PAE and major complication of AF ablation.

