5 ANALYSIS SETS

5.1 Main Phase

For the analysis of study endpoints, the analysis sets defined in the following will be used:

- **Full Analysis Set (FAS):** The FAS will consist of all enrolled subjects who have had insertion of the study catheter (with or without delivery of pulse field ablation [PFA]).
- **Modified Intent-To-Treat (mITT) Analysis Set:** The mITT analysis set will consist of enrolled subjects who have had insertion of the study catheter and meet eligibility criteria.

- **Per Protocol (PP) Analysis Set:** The PP analysis set will consist of all enrolled subjects who satisfy the following criteria:
 - Have undergone ablation with the IRE ablation system.
 - Are treated for the study-related arrhythmia.
 - Are without major protocol deviations that would affect the scientific integrity of the primary safety and effectiveness data, including but not limited to the following:
 - Subjects found not meeting eligibility criteria
 - Use of the IRE ablation modality to ablate outside the PV region
 - Failure to check for entrance block for each targeted PV after adenosine/isoproterenol challenge

Eligible subjects treated with commercially available catheters for non-PV triggers that may arise during the index procedure or during repeat procedures occurring during the blanking period will be followed for the full duration of follow-up and will be evaluable for all endpoints in order to preclude potential bias that would arise from exclusion of these subject profiles from endpoint estimates.

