7.4.3 Handling of Missing Data

Missing data will be queried for reasons and handled on an individual basis.

- **Sample Size Selection Interim Analysis:** For the sample size selection interim analyses, subjects with incomplete follow-up data for the effectiveness endpoint will be censored at the time of their last follow-up visit, and only their observed partial follow-up time will contribute to the estimation of model parameters and compute the predictive probability of the effectiveness success.
- **Early Success Primary Safety Endpoint:** For the early success interim analysis of the safety endpoints, if a subject's 3-month follow-up is not complete but a PAE has occurred prior to 3-month follow-up, the subject will be considered as having an event. If a subject exits the study without completing their 3-month follow-up visit and the subject has not had a PAE, that subject will be excluded from the early success safety analysis.
- **Early Success Primary Effectiveness Endpoint:** For the early success interim analysis of the effectiveness endpoints, subjects with incomplete follow-up data will be censored at the time of their last follow-up visit (if event-free). For these subjects, only their observed partial follow-up time will contribute to the estimation of model parameters. Subjects who refuse the remote arrhythmia/holter monitoring device will be excluded from the early success effectiveness analysis.

- **Final Primary Safety Endpoint:** For the final primary safety analysis, if a subject does not have full 12 months of follow-up and the subject has had a PAE at any time during the follow-up, the subject will be considered an event. If a subject does not have 12 months of follow-up but has at least 3 months of follow-up (similar to early success interim), this subject's last observed status will be carried forward for the 12-month safety endpoint as a proxy. If a subject without a PAE does not have at least 3 months of follow-up, this subject will be considered as missing the primary safety endpoint and will be excluded from the final primary safety analysis.

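### The protocol stops follow-up at 3 months for subjects given PFA plus RF for a non-PV arrhythmia, but both SAPs rely on their full 12-month data

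*Protocol*

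**What the plan says.** Protocol 14.2.2.2, under ablation outside the PV region, covers an arrhythmia that needs non-PV ablation and is identified after insertion of the study catheter. The subject has PVI with the study device, then commercial RF. The subject remains evaluable for acute success but is "excluded from the long-term effectiveness cohort and followed till 3-months post procedure". A note extends observation past month 3 only for adverse events already ongoing at that point.

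Protocol 8.1 states, without exception, "All study subjects will be followed though 12 months post-ablation".

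Wave I SAP section 5 and Wave II SAP section 5.1 address eligible subjects treated with commercial catheters for non-PV triggers, at the index procedure or at a repeat procedure in the blanking period. These subjects "will be followed for the full duration of follow-up and will be evaluable for all endpoints". The stated reason is to avoid the bias that excluding them would cause.

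On safety, protocol 8.2.1 says that device- or procedure-related death, PV stenosis and atrio-esophageal fistula "that occur greater than one week (7 days) post-procedure are considered and analyzed as PAEs". Table 6 defines the death component as "Subject death directly related to the device or procedure and occurs at any time during or after the procedure". For the final safety analysis, Wave II SAP 7.4.3 says that where follow-up is at least 3 but under 12 months, "this subject's last observed status will be carried forward for the 12-month safety endpoint as a proxy". Protocol 20.4.4.4 instead excludes an event-free subject with under 12 months.

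**The concern.** These subjects have received the full study treatment and belong to the mITT set, on which the primary safety endpoint is tested. A SAP can say how data are analysed, but it cannot create visits that the protocol tells sites not to make. If sites follow 14.2.2.2, the 6- and 12-month visits and the arrhythmia monitoring are lost and cannot be recovered at analysis.

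Two things are at stake. One is whether the primary effectiveness result covers the subjects the SAPs say it covers. The other is whether the final 12-month safety rate, and the late-onset SAE rate, rest on observed time for every treated subject. The 3-month limit is also the one that protocol 10.3 applies to discontinued subjects, who received no PFA energy at all.

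**Working it through.** **1. The texts side by side**

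| Question | Protocol | SAPs |
|---|---|---|
| Follow-up | 3 months (14.2.2.2); 12 months for all subjects (8.1) | Full duration (Wave I section 5; Wave II 5.1) |
| Long-term effectiveness | Excluded (14.2.2.2) | Evaluable for all endpoints |
| Per-protocol set | Removed if any ablation outside the PV region was required (20.3.2) | Removal named only for use of the IRE modality outside the PV region (Wave II 5.1) |
| Final safety, event-free, 3 to under 12 months | Excluded (20.4.4.4) | Wave II: last status carried forward (7.4.3). Wave I: excluded only if under 3 months (7.4.3) |

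**2. Effectiveness if sites stop at month 3**

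The evaluation period is Day 91-365, which is 365 - 90 = 275 days. The 3-month visit window is Day 76-104. A subject who stops there contributes at most 104 - 90 = 14 days, or 14/275 = 5% of the period, and none if seen by Day 90. At the early-success interim such a subject is censored there and informs at most the first two-week segment of the piecewise model. At the final analysis, Wave II SAP 7.4.3 treats an event-free subject with under 335 days as missing and drops that subject, while an acute procedural failure still counts.

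The documents give no rate of non-PV ablation. Assuming 2-10%, the affected number is 3.6-18 of 180, or 6.6-33 of 330.

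**3. Safety: the plan's own figure**

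Inputs are the Beta(1,1) prior, success if Pr(p < 0.14) > 0.975, a true rate of 7%, 5% dropout, and the Table 3.a shares at 65% effectiveness (0.5535, 0.2854 and 0.1611 for N = 180, 255 and 330). With evaluable n drawn from Binomial(N, 0.95), safety power is 0.8255, 0.9396 and 0.9818. The weighted value is 0.5535 x 0.8255 + 0.2854 x 0.9396 + 0.1611 x 0.9818 = 0.883, against 0.8853 in the SAP. The figure reproduces.

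**4. Safety: late events missed under carry-forward**

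Let s be the share of subjects affected (assumed 2-10%) and r their rate of a first PAE after month 3 (assumed 0.5-5%). Expected missed events are n x s x r. With a true rate of 14%, the observed rate is 0.14 - s x r, which runs from 0.1399 to 0.135. The chance of passing is Pr(Y <= c), where c is the largest event count that meets the success rule.

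| Evaluable n (95% of N) | c | Missed events | Pass at true 14%, full follow-up | Pass with carry-forward |
|---|---|---|---|---|
| 171 | 15 | 0.02-0.86 | 0.0262 | 0.0264-0.0392 |
| 242 | 23 | 0.02-1.21 | 0.0230 | 0.0233-0.0377 |
| 314 | 31 | 0.03-1.57 | 0.0180 | 0.0182-0.0321 |

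The 0.0262 is a value at one fixed n and reflects the discreteness of the rule; averaged over 5% dropout from 180 it is 0.021. One missed event changes the verdict only when the observed count sits exactly at c. For example, 15/171 gives a posterior probability of 0.9755 (pass) and 16/171 gives 0.9575 (fail).

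**5. Safety: exclusion under protocol 20.4.4.4**

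Removing 2%, 5% or 10% of 171 leaves 168, 162 or 154 subjects. Power at a 7% rate falls from 0.855 to 0.800, 0.836 and 0.809; the order is uneven because the limit moves in whole events.

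**6. Which analysis is affected**

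Protocol 20.4.4.2 bases the early-success safety test on 3-month follow-up for all mITT subjects, so the affected subjects are treated like the rest. In Table 3.a at 65% effectiveness, overall power is 0.8395 and early success 0.8316, so 0.8395 - 0.8316 = 0.0079 of simulated trials succeed only at the final analysis. The corresponding figures are 0.6749 - 0.6202 = 0.0547 at 60% and 0.8550 - 0.8547 = 0.0003 at 70%.

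**The case against.** The best defence is that 8.1 is a general statement and 14.2.2.2 a deliberate exception to it, that exclusion criterion 3 and the pre-insertion rule leave few such subjects, and that the formal safety decision is nearly always taken on 3-month data. All of that limits the size. None of it removes the conflict with the SAPs, which name these same subjects and promise full follow-up.

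Three stronger readings are tempting and are not supported:

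- **The plan scores unobserved late events as safe.** This follows only where the protocol's 3-month stop meets the carry-forward in Wave II SAP 7.4.3. Under the protocol alone these subjects leave the final safety analysis. Under the SAPs alone they have 12 months of data.
- **Dropping such subjects also helps the device.** Step 5 shows the reverse: losing event-free subjects makes success harder. Nor is it clear that a last visit on Day 76-90 leads to removal in Wave II, since the interim rule turns on completing the 3-month visit and the window allows those days.
- **Three quarters of follow-up lost means three quarters of safety information lost.** The 275 of 365 days is correct, but only three PAE types with onset after month 3 are at stake. Permanent phrenic nerve paralysis must be "documented to be present 12 months or longer following ablation", but a case still present at month 3 stays under observation through the note in 14.2.2.2. Wave I's scheduled PV imaging is at 3 months, inside the retained follow-up.

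**Conclusion.** The conflict is real and is a contradiction between documents about device-treated subjects. If sites follow 14.2.2.2, the SAPs' promise that these subjects are evaluable for all endpoints cannot be kept.

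The effectiveness consequence is the more direct one: event-free subjects are lost from the primary analysis whichever per-protocol definition is used. The safety consequence is limited to the final 12-month analysis and the reporting of late-onset SAEs. Under carry-forward it can only favour the device, but it is probably small: about 0.02 to 1.6 missed events. The chance of passing at a true 14% rate rises by 0.0002 at the low end and by about 0.013 to 0.015 at the high end. Those figures rest on the assumed 2-10% share and 0.5-5% late rate, neither of which is in the documents. The case for acting rests on data that cannot be recovered later, more than on a large expected shift.

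**What to change.** - Reconcile protocol 14.2.2.2 with protocol 8.1, Wave I SAP section 5 and Wave II SAP 5.1, so that the follow-up sites perform is the full duration on which the SAP analyses depend.
- Align protocol 20.3.2 with Wave II SAP 5.1 on per-protocol membership and effectiveness evaluability. Protocol 20.3.1 and 14.2.5 (non-PV repeat procedures in the blanking period) need the same check.
- Align protocol 20.4.4.4 with Wave II SAP 7.4.3, so that one missing-data rule governs the final safety analysis.
- For any subject already stopped at month 3, report actual follow-up time separately and include the subject in the best-case, worst-case and tipping-point analyses the Wave II SAP already plans.

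The cost is the 6- and 12-month visits with their monitoring for a small number of subjects (at the assumed upper end, 33 of 330, so 66 visits), plus short wording changes to the protocol and the Wave II SAP.
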